10.3.5 Pharmacodynamic Analyses

Exploratory Endpoint

Data from the exploratory biomarkers will be summarized descriptively by treatment and visit for the PD Analysis Set.

10.3.6 Pharmacokinetic / Pharmacodynamic Relationships

Exploratory Endpoint

Pharmacokinetic and PD endpoints will be explored graphically to evaluate potential relationships. These analyses will be performed on the PD Analysis Set. Population PK and PK / PD modelling may be used to further assess time-dependent characterization of PK versus PD endpoints, to be reported separately.

10.3.7 Other Analyses

Secondary Endpoint

The number of subjects with a positive immunogenicity test at any time posttreatment will be counted and compared between treatments with Fisher's Exact Test. The comparison will be of CSL346 (8 mg/kg and 16 mg/kg pooled) versus placebo. This analysis will be performed on the Safety Analysis Set.

Exploratory Endpoints

Exploratory endpoints will employ a model similar to the primary endpoint. The analysis for these continuous endpoints is an MMRM analysis of change from Baseline to each postbaseline measurement. The model will include treatment, stratification related to the concomitant use of SGLT2 inhibitors, visit (as a categorical factor), and interactions between visit and each of the other model terms, as well as the corresponding baseline measurement as a covariate. Exploratory urinary biomarkers will be normalized to creatinine level for analysis and reporting. Treatment comparisons of interest will be similar to that of the primary endpoint. These analyses will be performed on the PD Analysis Set.

The number of subjects who regress from macroalbuminuria to microalbuminuria or normoalbuminuria, or from microalbuminuria to normoalbuminuria at Week 16 will be counted and compared between treatments using Fisher's Exact Test. The comparison will be of CSL346 (8 mg/kg and 16 mg/kg pooled) versus placebo.

11 Quality Assurance

The study may be subject to an audit by CSL, an authorized representative(s) of CSL and / or inspections by an authorized health authority (eg, US Food and Drug Administration). Health authorities may request access to all study documentation, including source documents for

inspection and copying, in keeping with local regulations. CSL will notify the Investigator of any upcoming audit / inspection.

In the event of an audit, all pertinent study-related documentation must be made available to the auditor(s). If an audit or inspection occurs, the Investigator at each study site will permit the auditor / inspector direct access to all relevant documents and allocate their time as well as the time of relevant staff to discuss the findings and any relevant issues.

12 Regulatory and Ethics Considerations

12.1 Regulatory Considerations

CSL or its agents will submit the appropriate documents to the local regulatory agencies and will await approval before study start.

This study will be conducted under an US Food and Drug Administration Investigational New Drug application, Therapeutic Goods Administration Clinical Trial Notification, and the Health Research Council of New Zealand and documented in accordance with the applicable regulatory guidelines and requirements.

The procedures set out in this clinical study protocol are designed to ensure that CSL and the Investigator abide by the principles of the current ICH GCP guideline on the conduct, evaluation and documentation of this study, as described in ICH Topic E6 (Guideline for GCP). The study will also be carried out according to all applicable international and national regulatory requirements.

12.2 Institutional Review Board / Independent Ethics Committee

The Investigator must submit the clinical study protocol and ICFs for review by an authorized and properly constituted (according to local guidelines) IRB / IEC. Written approval must be received from the IRB / IEC before commencement of the study.

12.3 Subject Information and Informed Consent

Informed consent of subjects according to the standards of GCP and the principles in the Declaration of Helsinki must be implemented in this clinical study before protocol-specified procedures are carried out. Information should be given in both oral and written form and should be deemed appropriate by the IRB / IEC. Subjects, their relatives (or if necessary,

legally acceptable representatives) must be given ample opportunity to inquire about details of the study.

The subject (or if necessary, legally acceptable representatives) must be provided with a copy of the signed ICF.

Should there be any amendments to the clinical study protocol that would directly affect the subject's participation in the study (eg, a change in any procedure), the ICF must be amended to incorporate this modification. Subjects must be informed of the change and they must sign the amended ICF indicating that they re consent to participate in the study.

12.4 Subject Confidentiality

All subject names and contact details will be kept confidential. Subjects will be identified throughout documentation and evaluation by the number allotted to them during the study. Each subject will be told that all study findings will be handled in the strictest confidence.

The Investigator at the study site will be responsible for retaining sufficient information about each subject (eg, name, address, phone number, and identity in the study) so that regulatory agencies or CSL may access this information should the need arise. These records should be retained in a confidential manner as long as legally mandated according to local requirements.

Subject medical records pertaining to the study may be inspected / audited at any time by CSL employees or their duly authorized representatives, a health authority, or the IRB / IEC. All records accessed will be strictly confidential. Consent to participate in the study includes consent to these inspections / audits.

12.5 Indemnity and Compensation

CSL has taken out insurance to cover its obligations under both the Indemnity and the Compensation guidelines for injury to subjects involved in the study.

Other details regarding compensation and the obligations of the Investigator / CSL are provided in the Clinical Trial Research Agreement (CTRA) for the study (see [Section 13.1](#)).

13 Administrative Considerations

13.1 Clinical Trial Research Agreement

This study will be conducted under a CTRA between CSL (“Sponsor”) and the institution(s) representing the investigational study site(s) (“Authority”). Financial support to the investigational site(s) will be detailed in the CTRA. The CTRA must be signed before the commencement of the study and will clearly delineate the responsibilities and obligations of the Investigator and CSL, and will form the contractual basis under which the clinical study will be conducted. CTRAs may be executed by electronic signature (current provider DocuSign) in compliance with 21 CFR Part 11 and simple or advanced electronic signature according to EU Regulation No 910/2014 - eIDAS.

13.2 Clinical Study Registration and Results Disclosure

CSL will provide the relevant clinical study protocol information in public database(s) before or at commencement of the study. CSL may also provide study information for inclusion in national registries according to local regulatory requirements.

Results of this study will be disclosed according to the relevant regulatory requirements. All publications in peer-reviewed medical journals resulting from this study will be listed in the original clinical study protocol registration record.

13.3 Implementation of the Clinical Study Protocol and Amendment(s)

With the exception of medical emergencies, no changes or deviations in the conduct of the signed clinical study protocol will be permitted without documented approval of the CSL Medical Monitor or designee and the IRB / IEC. In the event of a medical emergency, the Investigator at the study site will institute any medical procedures deemed appropriate. However, all such procedures must be promptly reported to the CSL Medical Monitor and the IRB / IEC.

Modifications to the clinical study protocol that may affect subject safety or the way the study is to be conducted will be documented in a protocol amendment, which must be approved by the IRB / IEC.

Administrative changes to the clinical study protocol, defined as minor corrections and / or clarifications that have no effect on the way the study is to be conducted, will not require IRB / IEC approval, but will be submitted to the IRB / IEC for their information.

13.4 Protocol Deviations

All instances where the requirements of the clinical study protocol were not complied with will be tracked. Corresponding subjects may be withdrawn from the study at the discretion of the Investigator and / or CSL. Clinical study protocol deviations arise when either subjects who have been entered in the study and / or the study sites deviate from the IRB / IEC-approved study protocol.

If a major protocol deviation (ie, a deviation that could have a significant effect on the subject's safety, rights, or welfare and / or on the integrity of the study data) occurs, the Investigator must notify CSL and the appropriate IRB / IEC as soon as possible or as per local requirements.

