4.3 Discontinuation of Study Treatment and / or Subject Withdrawal

4.3.1 Reasons for Discontinuation of Study Treatment and / or Subject Withdrawal

Subjects may discontinue IP or withdraw from the study at any time at their own request, or at the discretion of the Investigator or CSL for safety, behavioral, or administrative reasons (eg, because of an AE, protocol deviation, loss to follow-up, subject noncompliance, study termination).

In accordance with the International Council for Harmonisation of Technical Requirements for Pharmaceuticals for Human Use (ICH) principles of Good Clinical Practice (GCP), the Investigator always has the option to advise a subject to withdraw from the study if the

subject's safety or wellbeing is compromised by his or her further participation in the study. Concern for the interests of the subject must always prevail over the interests of the study.

The Investigator should consult with the Medical Monitor before withdrawing subjects or discontinuing IP, then record the reason and date of subject withdrawal or discontinuation of IP in the eCRF and in the subject's medical records.

Refer to Section 4.3.2 for details on handling subject withdrawals.

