4.3.2 Procedures for Handling Withdrawals

If a subject is withdrawn from the study, attempts will be made to complete and document Follow-up Visits (Visit 10 and EOS). If the subject is unwilling or unable to return for Follow-up Visits, the site should attempt to collect AE information by telephone at 4 and 12 weeks after the last dose of IP.

If the subject is withdrawn from the study after receiving IP, every effort will be made to ensure that the relevant safety assessments are completed. The subject may also be asked by the Investigator to complete other study assessments.

If the subject withdraws from the study and also withdraws consent for disclosure of future information, CSL may retain and continue to use any data collected before such withdrawal of consent.

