7.3 Prohibited Therapies

The following therapies are NOT PERMITTED during the study:

Medication / Therapy	Dose	Prohibited Period of Use	Notes
Mineralocorticoid receptor antagonists, combination treatment with RAS inhibitors and ARB, or direct renin inhibitors ^a	NA	Within 8 weeks before Screening through EOS	NA
Trimethoprim, Cimetidine, Cephalosporins, Probenecid, Aminoglycosides, Ketoconazole, Clofibrate, Dronedarone, and Ranolazine.		Within 4 weeks before Screening through EOS	NA
Fenofibrate or nonsteroidal anti-inflammatory agents not taken as part of a stable regimen ^a		Within 8 weeks before Screening through EOS	NA
Immunosuppressive medications, such as cyclosporine, mycophenolate mofetil, tumor necrosis factor-alpha inhibitors, janus kinase inhibitors, or integrin receptor antagonists		Within 8 weeks before Screening through EOS	Systemic corticosteroids are only permitted at low doses for short-term treatment of acute conditions, such as an allergic reaction or gout
Other investigational agents ^a	N/A	Within 12 weeks before Screening through EOS	This is not applicable if the subject is known to have received a placebo as part of another clinical trial

^a If administration of any prohibited therapy becomes necessary during the study for medical reasons, the subject may be withdrawn from further study treatment and proceed to Follow-up (Section 4.3.2).

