### **10.1 Analysis of Primary Endpoint(s)**

#### **10.1.1 Primary Estimand**

The primary interest is to quantify the treatment effect of CSL346 under the situation where SGLT2i may be a possible effect modifier and is included in the model. The estimand for the ITT Analysis Set is the average effect of CSL346 on the geometric mean ACR at 16 weeks averaged across subjects receiving and not receiving SGLT2i. All data collected through Week 24 will be used in the analysis.

The primary estimand in line with the primary interest of the study is described as follows:

- Treatment Condition: four SC administrations of CSL346 or placebo over a 12-week period (Day 1, Weeks 4, 8 and 12) where the primary comparison is between CSL346 at Week 16, regardless of dose, and placebo, while subjects have not died. The “treatment policy strategy” will be used, i.e. changes in dose, for example from 16 mg/kg to 8 mg/kg OR the number of subcutaneous injections, or treatment discontinuation/non-initiation, or other miscellaneous factors influencing ACR will not be taken into account in the primary analysis;
- Population: the target patient population defined by T2DM and DKD and further eligibility criteria;

- Variable: change from baseline at 16 weeks of log ACR;
- Population-level summary: difference in treatments, calculated as  $100\% \times (\text{geometric mean ratio of the treatment comparison} - 1)$  based on log ACR.

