#### **10.4 Missing Data and Imputation**

To avoid missing data with regard to the primary endpoint, ACR, procedures will be in place to maximize the ability to collect first morning voids for every subject at every planned visit. Likewise, every attempt will be made to retain subjects in the study once they are randomized. Therefore, it is anticipated that missing data with regard to the primary endpoint will be kept to a minimum. Imputation is only being considered for the sensitivity analysis for the primary endpoint.

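### Protocol 13.4 and 4.3.1 permit withdrawal from the study, not only from treatment, for a protocol deviation, which can cause avoidable and possibly informative loss of Week 16 ACR

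*Protocol*

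**What the plan says.** **Withdrawal rules.** Protocol 13.4 covers every instance of non-compliance with the protocol, by subjects or by sites, and then says: "Corresponding subjects may be withdrawn from the study at the discretion of the Investigator and / or CSL". It defines a major deviation, but uses that term only for notification. Protocol 4.3.1 lets the investigator or sponsor stop product or withdraw a subject from the study for reasons such as "because of an AE, protocol deviation, loss to follow-up, subject noncompliance, study termination". It adds a check: "The Investigator should consult with the Medical Monitor before withdrawing subjects or discontinuing IP". That check is addressed to the investigator, not to the sponsor.

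**After withdrawal.** Protocol 4.3.2 says attempts will be made to complete Visit 10 and End of Study. If the subject will not return, the site tries to collect adverse event information by telephone, 4 and 12 weeks after the last dose.

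**What the analysis needs.** The primary analysis uses the ITT set (SAP 6.2, 10.1.2) with a treatment-policy strategy. SAP 10.1.1 says that "treatment discontinuation/non-initiation, or other miscellaneous factors influencing ACR will not be taken into account in the primary analysis". On missing data, SAP 10.4 says: "Likewise, every attempt will be made to retain subjects in the study once they are randomized". It reserves imputation for the sensitivity analysis.

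**How deviations are handled elsewhere.** Under the footnote to Protocol 7.3, if a marked prohibited therapy becomes necessary, "the subject may be withdrawn from further study treatment and proceed to Follow-up". Several parts of Protocol 9.1.3 ask sites to keep subjects in follow-up after product stops. SAP 10.1.3 and 16.7 deal with deviations by removing later data from the Per-Protocol set.

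**The concern.** Under a treatment-policy estimand, a Week 16 ACR measured after a deviation is wanted data. Withdrawing the subject from the study puts that value at risk, and it serves no analytic purpose because the Per-Protocol analysis already removes post-deviation data.

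SAP 16.7 lists events such as substantial changes in blood pressure or kidney disease drugs, prohibited medication and changes in SGLT2 inhibitor dose as factors that may affect ACR. If such an event leads to withdrawal, the missing value is plausibly related to the outcome. The primary MMRM would then treat it as missing at random. The SAP's tipping-point analysis runs on the Per-Protocol set (SAP 10.1.3), so nothing in the plan tests the ITT result against informative missing data. Preventing the loss is the most direct remedy.

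**Working it through.** **1. Reproduce the design.** Inputs from Protocol 10.1 and SAP 4.4: SD 0.65, 27% reduction, one-sided alpha 0.10, 94 completers, 6% drop-out.
- Effect: ln(0.73) = -0.3147.
- Standard error at 47 per group: 0.65 × √(2/47) = 0.1341.
- Power, normal approximation: Φ(0.3147/0.1341 − 1.2816) = 85.7%. The noncentral t gives 85.4%. The plan states 85%.
- Critical difference from the t distribution: 0.173, as stated.
- Randomized: 94/0.94 = 100, as stated.

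**2. Power if more Week 16 values are lost.** The documents give no rate of deviation-driven withdrawal, so total loss is an assumed range. Power counts completers only, by normal approximation, with 100 randomized and no top-up.

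| Total loss | Completers | Power | Randomized to hold 94 (94/(1 − loss), rounded up) |
|---|---|---|---|
| 6% | 94 | 85.7% | 100 |
| 8% | 92 | 85.1% | 103 |
| 10% | 90 | 84.5% | 105 |
| 15% | 85 | 82.9% | 111 |
| 20% | 80 | 81.2% | 118 |

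Each further 2 subjects lost cost about 0.6 points (85.7 to 85.1 to 84.5). The cap of 124 absorbs total loss up to 1 − 94/124 = 24.2%. Counting completers only somewhat overstates the cost, because the MMRM also uses earlier visits.

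**3. Illustrative bias.** Assume 10% of an arm is lost and that those subjects' true Week 16 log change is 0.3 worse than missing-at-random predicts. The arm mean is then wrong by 0.10 × 0.3 = 0.03. The contrast is 0.5 × (8 mg/kg + 16 mg/kg) − placebo, so:
- One CSL346 dose arm only (2.5 of 25 subjects): 0.5 × 0.03 = 0.015, and 0.015/0.173 = 9% of the significance boundary, in favour of CSL346.
- Both CSL346 arms: 0.03, or 0.03/0.173 = 17%, in favour of CSL346.
- Placebo only: 0.03, or 17%, against CSL346.
- Equal loss of the same kind in all arms: the shifts cancel.

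**4. Does 4.3.2 secure the Week 16 value?** In the schedule, Visit 10 is Day 113. For a subject who receives all doses it is also 4 weeks after the last dose (Day 85 + 28), and Protocol 8.1.3 describes it that way. For a subject who stops early the two definitions separate: with a last dose on Day 29, 4 weeks later is Day 57. Section 4.3.2 does not say which applies to Visit 10, and it times its telephone fallback from the last dose. SAP 8.2.5 applies no visit windows and places data collected at study discontinuation at the closest scheduled visit, which need not be Week 16.

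**The case against.** The strongest reply is that the protocol already handles this. Section 4.3.2 applies to subjects withdrawn from the study and seeks Visit 10, the primary ACR visit. The 7.3 footnote refers to the same section, so both routes lead towards Visit 10 and End of Study. Section 13.4 is permissive, and the investigator should consult the Medical Monitor first. SAP 10.4 is itself a best-effort statement. SAP 16.7 removes post-deviation data from the Per-Protocol set, which presupposes that such subjects usually stay and keep providing urine samples. Investigators and sponsor staff are blinded, with limited exceptions (Protocol 6.3), so withdrawal that differs by arm is less likely.

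Most of this stands, and it rules out two stronger readings that a reader might infer. The first is that 13.4 creates missing Week 16 data. It only permits a step that can lead to missing data, and 4.3.2 tries to recover them. The second is that 13.4 contradicts the estimand. SAP 10.1.1 says how events are treated in the analysis; it does not govern who may be withdrawn.

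Nor do the documents support a claim of serious power loss. The top-up allowance covers the plausible range. Moreover, a completer must have received all doses, so a subject who misses doses does not count towards 94 even if retained.

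What the reply does not remove is the gap in 4.3.2: attempts only, no fixed day, and no ACR in the fallback. Blinding limits differential loss but does not exclude it.

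**Conclusion.** The point holds as a tension between sections, of minor to moderate weight. Protocol 13.4 and 4.3.1 allow removal from the study for any deviation, while the ITT treatment-policy analysis wants those subjects' ACR and SAP 10.4 relies on keeping them. Any Week 16 value lost this way is avoidable and may be informative.

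The sample size is unaffected. The case for change rests on bias, which extra randomization does not cure. Its size cannot be estimated from the documents: the 0.015 and 0.03 shifts rest wholly on the assumed 10% loss and 0.3 log-unit departure, and on the loss being unequal between arms. For comparison, the plan assumes 6% drop-out in total.

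**What to change.** In Protocol 13.4 and 4.3.1, state that a protocol deviation alone is not a reason to withdraw a subject from the study. Such subjects stay on the visit schedule, with first-morning-void ACR collected at Week 16 (Day 113) and Week 24 (Day 169), counted from randomization. Cross-refer to 4.3.2, and add the same days there so that Visit 10 and End of Study are not timed from the last dose.

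Leave unchanged all existing rules on continuing or stopping investigational product, withdrawal of consent, loss to follow-up, withdrawal for safety, pregnancy and breastfeeding (9.6.6), and study termination. The new text should not offer a closed list of permitted withdrawal reasons, because omitting any of these would create a new conflict.

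The cost is one sentence in each of two sections, a matching clause in 4.3.2, a few more scheduled visits for subjects with deviations, and less discretion for the investigator and sponsor to withdraw them.

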13.5 Documentation and Record Keeping

13.5.1 Data Collection

The Investigator (or delegate) will maintain individual records for each subject. These records should include dates when a subject visited the study site, records of vital signs, medical history, physical examinations, administration of IP or concomitant therapy, any AEs experienced, and other notes as appropriate. These records (electronic or paper) constitute source data.

Electronic case report form entries will be considered source data if the eCRF is the site of the original recordings (ie, there is no other written or electronic record of the data).

An eCRF will be provided by CSL (or delegate) for each subject enrolled into the study. The Investigator is responsible for ensuring accurate and proper completion of the eCRF in a timely manner so that it always reflects the latest observations on the subjects enrolled in the study. All entries on the eCRF must be backed up by source data unless the eCRF is considered source data. All source data will be kept according to all applicable regulatory requirements. Source data must be completed legibly for each subject enrolled into the study and signed by the Investigator (or delegate).

